## 8.2 Background Characteristics

### 8.2.1 Subject Disposition

#### Part A and Part B

Subject disposition will be summarized for the All Subjects Set for corresponding part.

Number of subjects in the following categories will be summarized:

- All Subjects Set
- Safety Set
- Never dosed

The number and percentage (based on the Safety Set) of subjects in each of the following disposition categories will be summarized:

- Completed Treatment

- Prematurely discontinued treatment and the reasons for discontinuation
- Completed study
- Prematurely discontinued the study and the reasons for discontinuation
- Departed Study VX18-445-113 to participate in another qualified Vertex study
- Departed Study VX18-445-113 to participate in another qualified Vertex study and returned to VX18-445-113
- Subjects rolled over to Part B (for Part A only).

A listing will be provided by part, for subjects who discontinued treatment or who discontinued study with reasons for discontinuation. A separated listing will be provided by part for subjects who departure from the study.

## **8.2.2 Demographics and Baseline Characteristics**

### **Part A and Part B**

Demographics and baseline characteristics will be summarized based on the Safety Set for corresponding part.

Demographic data will include the following:

- Age at baseline (in years)
- Sex (female and male)
- Ethnicity (Hispanic or Latino, not Hispanic or Latino, and not collected per local regulations)
- Race (White, Black or African American, Asian, American Indian or Alaska Native, Native Hawaiian or Other Pacific Islander, Not Collected per Local Regulations and Other)
- Geographic region (North America, Europe [including Israel and Australia])

Baseline characteristics will include the following:

- Weight (kg)
- Height (cm)
- BMI (kg/m^2)

Disease characteristics will include the following:

- ppFEV1 at baseline (<40, ≥ 40 to <70, ≥70 to ≤90, and >90)
- ppFEV1 at baseline (continuous)
- Prior use of dornase alfa (Yes, No)
- Prior use of azithromycin (Yes, No)
- Prior use of inhaled antibiotic (Yes, No)
- Prior use of any bronchodilator (Yes, No)
- Prior use of any inhaled bronchodilator (Yes, No)

- Prior use of any inhaled hypertonic saline (Yes, No)
- Infection with *Pseudomonas aeruginosa* within 2 years prior to screening visit of VX-659 in VX17-659-102 or VX17-659-103 (Positive, Negative)

In addition, data listings will also be provided for:

- Informed consent;
- Inclusion/Exclusion criteria violation for subjects with any such violations.

### 8.2.3 Medical History

Medical history will be summarized separately for Parts A and B based on the Safety Set.

#### Part A and Part B

Medical history will be coded by using the Medical Dictionary for Regulatory Activities (MedDRA).

Medical history will be summarized descriptively by System Organ Class (SOC) and Preferred Term (PT) based on the Safety Set for the corresponding part. The corresponding data listing will also be provided.

### 8.2.4 Prior and Concomitant Medications

Prior and concomitant medications will be summarized separately for Parts A and B based on the Safety Set.

#### Part A and Part B

Medications will be coded using the World Health Organization-Drug Dictionary (WHO-DD) and categorized as follows:

- **Prior medication:** any medication that was administered during the 56 days before the first dose of study drug in the corresponding part. For subjects who enroll in another qualified Vertex study before completing this study and resume participation in this study, any new or changed medication administered after the Departing Visit and prior to the first dose of this study's study drug after resuming participation will also be considered prior medication.
- **Concomitant medication:** medication continued or newly received during the TE Period in the corresponding part.
- **Post-treatment medication:** medication continued or newly received after the TE Period in the corresponding part.

A given medication may be classified as a prior medication, a concomitant medication, or a post-treatment medication; both prior and concomitant; both concomitant and post-treatment; or prior, concomitant, and post-treatment.

If a medication has completely missing or partially missing start/stop date and if it cannot be determined whether it was taken before the first dose date, concomitantly during the TE Period, or after the TE Period, it will be considered in all 3 categories of prior, concomitant, and post-treatment medication. Details for imputing missing or partial start and/or stop dates of medication are described in [Appendix B](#).

Prior medications and concomitant medications will be summarized descriptively using frequency tables based on the Safety Set by: 1) preferred name (PN); and 2) Anatomical

Therapeutic Chemical (ATC) level 1, ATC level 2, and PN. All medications will be listed for each subject.

### **8.2.5 Study Drug Exposure**

Exposure summaries will be separated for Parts A and B based on the Safety Set.

#### **Part A and Part B**

Duration of study drug exposure (in days) will be calculated as: last dose date of study drug in the corresponding part – first dose date of study drug in the corresponding part + 1, regardless of study drug interruption.

For subjects who enroll in another qualified Vertex study before completing this study and resume participation in this study, time spent in the other study will be excluded.

Study drug exposure (in weeks) will be summarized descriptively by the number of subjects (n), mean, SD, median, min, and max. It will also be summarized into the following categories:  $\leq 24$  weeks,  $>24-\leq 48$  weeks,  $>48-\leq 72$  weeks,  $>72-\leq 96$  weeks,  $>96$  weeks for Part A;  $\leq 24$  weeks,  $>24-\leq 48$  weeks,  $>48$  weeks for Part B.

Additionally, the total study drug exposure, defined as the sum of the study drug exposure across all subjects (in patient-weeks and patient-years), will be provided.

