### **3 SCHEDULE OF ASSESSMENTS**

The schedule of assessments is provided in [Table 3-1](#). All visits will be scheduled relative to the Day 1 Visit in this study.

Assessments may be performed in any order when more than 1 assessment is required at a particular time point. All assessments will be performed before study drug dosing (Section 9.6.1), unless noted otherwise.

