**Table 3-1 VX18-445-113: Treatment Period and Safety Follow-up Visit**

Event/Assessment a	Treatment Period							ETT Visit b	Safety Follow-up Visit (28 ± 7 Days After Last Dose) c	Comments
	Day 1 d	Day 15 (± 3 Days)	Weeks 4, 8, 16, 24, 36 (± 5 Days)	Weeks 12, 20, 28, 32, 40, 44, 52, 56, 64, 68, 76, 80, 88, 92 (± 5 Days)	Week 48 (± 5 Days)	Weeks 60, 72, 84 (± 5 Days)	Week 96 (± 5 Days)			
Hematology	X	X	X		X	X	X	X	X	
Coagulation	X		Week 24		X	Week 72	X	X	X	
Serum chemistry	X	X	X		X	X	X	X	X	
Study drug count	X	X	X		X	X	X	X		Section 10.6
Study drug dosing	Day 1 through evening before Week 96 Visit									Subjects on study drug interruption from Study 659-105 may NOT begin dosing until they meet the criteria in Section 9.8. Refer to Section 9.6.1 for study drug administration details.
Medications review	Continuous from signing of the ICF (or assent form) through completion of study participation									Completion of study participation is defined in Section 9.1.5.
Treatments and procedures review	Continuous from signing of the ICF (or assent form) through completion of study participation									
AEs and SAEs	Continuous from signing of the ICF (or assent form) through completion of study participation									

AE: adverse event; ETT: Early Termination of Treatment; FSH: follicle-stimulating hormone; ICF: informed consent form; SAE: serious adverse event; SwCl: sweat chloride

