## 9.6 Administration

### 9.6.1 Dosing

Study drug will be administered orally. Additional information is provided in the Pharmacy Manual.

Study drug will be administered with a fat-containing meal or snack, such as a standard “CF” meal or snack or a standard meal.

1. It is recommended that the dose be taken within 30 minutes of the start of the meal or snack.
2. Study drug will be administered as 2 fixed-dose combination (FDC) VX-445/TEZ/IVA TC tablets in the morning and as 1 IVA tablet in the evening. For each subject, doses of study drug will be taken at approximately the same time ( $\pm 2$  hours) each day.
3. The last dose of FDC VX-659/TEZ/IVA TC tablets from Study 659-105 should be taken the day prior to the Day 1 Visit for Study 445-113. The first dose of FDC VX-445/TEZ/IVA TC tablets should be administered in the clinic.

Doses of FDC VX-445/TEZ/IVA TC and FDC VX-659/TEZ/IVA TC should **not** be taken on the same day. If the first dose of FDC VX-445/TEZ/IVA TC tablets is not taken until the afternoon of Day 1, then the subject should skip their evening dose of IVA on Day 1 and subsequently take their second dose of FDC VX-445/TEZ/IVA TC tablets the morning of Day 2 and their first evening dose of IVA the evening of Day 2.

If the subject inadvertently takes their last dose of FDC VX-659/TEZ/IVA TC tablets from Study 659-105 on the morning of the planned Day 1 Visit for Study 445-113, then the subject should take the first evening dose of IVA on Day 1 and the first dose of FDC VX-445/TEZ/IVA TC tablets the morning of Day 2.

4. On days of scheduled visits, the morning dose of VX-445/TEZ/IVA will be administered at the site after predose assessments have been completed. A meal or snack will be provided by the site for the morning dose of VX-445/TEZ/IVA.

5. If a subject's scheduled visit is to occur in the afternoon, the following guidelines must be used:
  - If the dose in the clinic will be within 6 hours of the subject's scheduled morning dose, the subject should withhold their morning dose of VX-445/TEZ/IVA and the morning dose of VX-445/TEZ/IVA will be administered in the clinic.
  - If the dose in the clinic will be more than 6 hours after the subject's scheduled morning dose of VX-445/TEZ/IVA, the subject should take the morning dose of VX-445/TEZ/IVA at home.
6. Subjects will be instructed to bring all used and unused materials associated with study drug to the site; study drug will be dispensed at each visit, as appropriate.

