## 11 APPENDICES

### Appendix A: Analysis Visit Windows for Safety Assessments

Table 11-1 Analysis Visit Windows for Safety Assessments			
Assessment	Visit	Target Study Day	Analysis Visit Window (in study days)
Part A			
Spirometry Serum Chemistry Hematology Vital Signs  Pulse Oximetry	Baseline	1	defined in section 8.1
	Day 15	15	[1, 22] where day 1 is post-dose measurement
	Week 4	29	(22, 43]
	Week 8	57	(43, 85]
	Week 16	113	(85, 141]
	Week 24	169	(141, 211]
	Week 36	253	(211, 295]
	Week 48	337	(295, 379]
	Week 60	421	(379, 463]
	Week 72	505	(463, 547]
	Week 84	589	(547, 631]
	Week 96	673	(631, 687]
	Safety Follow-up 	Not applicable	Use nominal visit
Standard 12-lead ECG	Baseline	1	defined in section 8.1
	Day 15	15	[1, 36] where day 1 is post-dose measurement
	Week 8	57	(36, 113]
	Week 24	169	(113, 253]
	Week 48	337	(253, 421]
	Week 72	505	(421, 589]
	Week 96	673	(589, 687]
	Safety Follow-up 	Not applicable	Use nominal visit
Coagulation	Baseline	1	defined in section 8.1
	Week 24	169	[1, 253] where day 1 is post-dose measurement
	Week 48	337	(253, 421]
	Week 72	505	(421, 589]
	Week 96	673	(589, 687]
		Safety Follow-up 	Not applicable

Table 11-1 Analysis Visit Windows for Safety Assessments			
Assessment	Visit	Target Study Day	Analysis Visit Window (in study days)
Weight, Height and BMI	Baseline	1	defined in section 8.1 [1, 43] where day 1 is post-dose measurement (43, 85] (85, 141] (141, 211] (211, 295] (295, 379] (379, 463] (463, 547] (547, 631] (631, 687] Use nominal visit
	Week 4	29	
	Week 8	57	
	Week 16	113	
	Week 24	169	
	Week 36	253	
	Week 48	337	
	Week 60	421	
	Week 72	505	
	Week 84	589	
	Week 96	673	
	Safety Follow-up 	Not applicable	
Sweat Chloride (Clinic collected only)	Baseline	--	defined in section 8.1 [1, 421] where day 1 is post-dose measurement (421, 687]
	Week 24	169	
	Week 96	673	
Sweat Chloride (collected at unscheduled home visits)	Home SwCl collection visit 1	Not applicable	Use nominal visit 
	Home SwCl collection visit 2	Not applicable	Use nominal visit 
Part B			
Spirometry Serum Chemistry Hematology Vital Signs  Weight, Height and BMI Pulse Oximetry	Baseline	--	defined in section 8.1 [1, 127] where day 1 is post-dose measurement (127, 211] (211, 295] (295, 351] Use nominal visit
	Part B Week 12	85	

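### Does the 96-week exposure break in SAP 8.2.5 put subjects who complete Part A in the wrong class?

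*SAP*

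**What the plan says.** SAP 8.2.5 defines exposure in days as "last dose date of study drug in the corresponding part – first dose date of study drug in the corresponding part + 1", counted "regardless of study drug interruption". It is then summarised in three ways: descriptive statistics in weeks (n, mean, SD, median, minimum, maximum); a frequency table with Part A breaks at 24, 48, 72 and 96 weeks, ending in ">96$ weeks for Part A"; and total exposure in patient-weeks and patient-years. A value of exactly 96 weeks belongs to the class below the last break.

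Protocol Table 3-1 gives the dosing period as "Day 1 through evening before Week 96 Visit" and allows ±5 days around that visit. SAP Appendix A sets the Week 96 target at study day 673. Protocol Section 3 anchors the calendar: "All visits will be scheduled relative to the Day 1 Visit in this study". Protocol 9.3.2 plans treatment of up to 96 weeks.

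Protocol 9.6.1, item 4, has a general rule for visit days: "On days of scheduled visits, the morning dose of VX-445/TEZ/IVA will be administered at the site after predose assessments have been completed".

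SAP 8.2.1 reports, by part, how many subjects completed treatment, and also "Prematurely discontinued treatment and the reasons for discontinuation", with a listing of those who discontinued.

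**The concern.** A reader may take the top class of an exposure table as the group that had the full planned treatment. Here it is not. A subject who follows the Part A schedule exactly has 96.0 weeks and just misses the top class, while one who attends a day late enters it. The class below also holds subjects who stopped soon after Week 72, almost 24 weeks earlier. Protocol 9.3.2 justifies the study by its 96-week duration, so a table that cannot separate near-complete exposure from exposure ending well short of it seems to hide the very thing a long-term safety study should show. At stake would be a misleading picture of how many subjects had about 96 weeks of treatment.

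**Working it through.** **Inputs.** Exposure formula and breaks: SAP 8.2.5. Target day 673: SAP Appendix A. Window ±5 days and end of dosing: Protocol Table 3-1. First dose on Day 1: Protocol 9.1.1, for subjects who do not enter on a drug interruption.

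**1. The plan's own figure.** Week 96 target day = 96 × 7 + 1 = 673, which agrees with Appendix A. In days, the last break is 96 × 7 = 672.

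**2. Exposure of a completer, last dose the evening before the visit.** Exposure = (visit day − 1) − 1 + 1 = visit day − 1.

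- Earliest in-window visit, Day 668: 667 days; 667/7 = 95.29 weeks.
- On target, Day 673: 672 days; 672/7 = 96.00 weeks.
- Latest in-window visit, Day 678: 677 days; 677/7 = 96.71 weeks.

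Visits on Days 668 to 673 (6 of 11) give 672 days or fewer. Visits on Days 674 to 678 (5 of 11) give more.

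**3. The other reading of the last dose.** If the last dose is taken at the site on the visit day, as Protocol 9.6.1 item 4 could be read, exposure = visit day. The range is 668 to 678 days (95.43 to 96.86 weeks), with 5 of 11 days at or below the break and 6 above. Table 3-1 and item 4 should be reconciled in their own right, but the break lies inside the range under both.

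**4. Share of in-window completers at or below 96.0 weeks.** The documents give no distribution of visit days, so these are assumptions. The normal distributions are discretised by day and truncated to the window.

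| Visit timing | Last dose evening before | Last dose on visit day |
|---|---|---|
| Even over the window | 6/11 = 54.5% | 5/11 = 45.5% |
| Centred on target, SD 2 days | 59.9% | 40.1% |
| Centred on target, SD 3 days | 57.1% | 42.9% |

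If visits average two days early or late (SD 2), the share under the first reading runs from about 24% to 89%. These are shares of an unknown number of completers.

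**5. Is anyone put in the wrong class?** A subject with 667 to 671 days has less than 96 weeks and is placed at or below 96. A subject with 673 to 677 days has more than 96 weeks and is placed above. A subject with exactly 672 days has 96.0 weeks and is placed in the class whose upper limit includes 96. All eleven values match their labels.

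**6. Is the mixture in the class below unusual?** It runs from 72 × 7 + 1 = 505 days to 672 days, a spread of 167 days (23.9 weeks). The class above 24 and up to 48 weeks runs from 169 to 336 days, also 167. The class above 48 and up to 72 weeks runs from 337 to 504 days, again 167. Such a spread comes with any 24-week grid.

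**7. What uses the break?** Mean, SD, median, minimum, maximum, patient-weeks and patient-years are computed from days of exposure. Completed and discontinued treatment are counted from disposition. Neither these nor the exposure-adjusted event rates refer to the 96-week class limit. Only the counts in the top two rows of one table depend on it.

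**The case for a change.** The strongest case for a change is that the three lower breaks do not coincide with a planned end of treatment, whereas the last one cuts a cluster that the protocol itself creates. Readers want to know how many subjects had about 96 weeks, and no single Part A row tells them. Disposition gives the number of completers but not their exposure. A break at 95 weeks (665 days) would sit below all eleven in-window values under either reading of the last dose (minimum 667 or 668), and it would cost one line before database lock.

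The arithmetic stands. So does the caution that the top class must not be read as the completers. The rest does not make the plan wrong:

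- **The grid says what it counts.** With treatment planned for up to 96 weeks, a class that ends at and includes 96 holds the planned duration, and the class above it shows overrun. That is a coherent way to tabulate.
- **The alternative is a preference.** A 95-week cut is off the grid, gives up the count above 96 weeks, and puts completers together with subjects who discontinue from Day 665 onward.
- **It would not capture every completer.** SAP 8.2.5 subtracts time spent in another study for subjects who leave and return, so a subject who starts on Day 1 and attends Week 96 in window can have fewer than 665 days. Exposure also stops at the last dose date, so an interruption in the final weeks shortens it even though earlier interruptions are ignored.
- **How many subjects it concerns is unknown.** Protocol 9.9 allows discontinuation when commercial product becomes available, and the COVID-19 addendum (Version 3.0) permits unscheduled visits even after the last scheduled one. Neither the number of completers nor the number seen in window can be derived.

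**Conclusion.** The concern does not hold. The 96-week break does fall inside the range of in-window completers: 667 to 677 days, or 668 to 678 if the last dose is on the visit day. A one-day change in visit can move a subject to the next row. But the classes are exclusive, exhaustive and correctly labelled, no stated figure or rule is wrong, and the SAP attaches no meaning of completion to the top class. The effect is confined to two rows of one descriptive table. The continuous exposure summary, total patient-years, exposure-adjusted event rates and disposition counts are the same wherever the break is placed.

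This rests on the US protocol's Part A schedule, since the regional protocol with Part B was not supplied, and on subjects who start on Day 1, dose continuously to the end and have a known last dose date. Other subjects may have less exposure, but they too are classed by the exposure they had. Where the SAP imputes a missing last dose date, the class follows the imputed date.

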### **8.2.6 Study Drug Compliance**

Study drug compliance will be summarized separately for Parts A and B based on the Safety Set.

#### **Part A and Part B**

Study drug compliance will be calculated as:  $100 \times [1 - (\text{total number of days of study drug interruption}) / (\text{duration of study drug exposure in days})]$ . A study drug interruption on a given day is defined as an interruption of any study drug on that day. For subjects who participate in another qualified Vertex study before completing Study VX18-445-113 and resume participation in Study VX18-445-113, time spent in the other study will be excluded.

Study drug compliance will be summarized descriptively by the number of subjects (n), mean, SD, median, min, and max. It will also be summarized in categories:  $<80\%$  and  $\geq 80\%$  using frequency tables.

In addition, percentage of tablets taken will be calculated as  $100 \times [(\text{total number of tablets dispensed}) - (\text{total number of tablets returned})] / (\text{total number of tablets planned to be taken per day} \times \text{duration of study drug exposure in days})$ . A summary similar to that for study drug compliance will be produced.

### **8.2.7 Important Protocol Deviations**

Important protocol deviation (IPD) will be summarized separately for Parts A and B based on the Safety Set.

#### **Part A and Part B**

An IPD is a deviation that may significantly affect the completeness, accuracy, or reliability of the study data or that may significantly affect a subject's rights, safety, or well-being. A protocol deviation review team will categorize IPDs according to the protocol deviation plan during the study.

Protocol deviations that should be considered as potential IPDs include, but are not limited to:

- Subject was enrolled in the study despite not satisfying one or more inclusion/exclusion criterion
- Subject was less than 80% compliant with study drug for non-safety reasons
- Subject received prohibited concomitant medications
- Subject received the wrong treatment or incorrect doses.

IPDs will be summarized descriptively based on Safety Set for Part A and Part B separately. Additionally, IPDs will be provided in an individual subject data listing based on Safety Set for Part A and Part B separately.

### **8.3 Efficacy Analysis**

Not applicable.

### **8.4 Safety Analysis**

The primary objective of the study is the evaluation of the long-term safety and tolerability of ELX/TEZ/IVA. Safety analysis will be summarized separately for Parts A and B. Part A safety analyses will be based on the TE Period for Part A for subjects in the Safety Set for Part A. Part B safety analyses will be based on the TE Period for Part B for subjects in the Safety Set for Part B. The overall long-term safety profile of study drug will be assessed in terms of the following safety and tolerability endpoints:

- Treatment-emergent adverse events (TEAEs)
- Clinical laboratory values (i.e., serum chemistry, hematology, coagulation, and urinalysis)
- ECGs
- Vital signs including body weight and BMI
- Pulse oximetry
- Spirometry

Only descriptive analysis of safety will be performed, and no statistical testing will be performed.

#### **8.4.1 Adverse Events**

Summaries of TEAEs will be provided separately for Parts A and B based on the Safety Set.

For analysis purposes, AEs will be classified as pretreatment AEs, TEAEs, or post-treatment AEs for the corresponding part, defined as follows:

- **Pretreatment AE:** any AE that occurred before the first dose date of study drug in the TE Period in the corresponding part. For subjects who enroll in another qualified Vertex study before completing this study and resume participation in this study, AEs that started during participation in another qualified Vertex study and are ongoing at the time of Returning Visit will be flagged as pre-treatment AE.

- **TEAE:** any AE that worsened (either in severity or seriousness) or newly developed at or after the first dose date of study drug in the TE Period in the corresponding part.
- **Post-treatment AE:** any AE that worsened (either in severity or seriousness) or that was newly developed after the TE period in this study in the corresponding part.

For AEs with completely missing or partially missing start dates, if there is no clear evidence that the AEs are pre-treatment or post-treatment, the AEs will be classified as TEAEs.

Details for imputing missing or partial start dates of adverse events are described in [Appendix C](#).

An overview of all TEAEs will be provided with the following categories separately for Parts A and B:

- Number of TEAEs (total number of TEAEs only)
- Subjects with any TEAEs
- Subjects with TEAEs by strongest relationship
- Subjects with TEAEs by maximum severity
- Subjects with TEAEs leading to study drug discontinuation (discontinuation of any study drugs)
- Subjects with TEAEs leading to study drug interruption (discontinuation of any study drugs)
- Subjects with Grade 3/4 TEAEs
- Subjects with related TEAEs
- Subjects with serious TEAEs
- Subjects with related serious TEAEs
- Subjects with TEAE leading to death

The frequency counts and percentages as well as the exposure adjusted event rate will be presented for the above overview table. The exposure adjusted rate will not be presented for strongest relationship and maximum severity categories.

The following summary tables of TEAEs will be presented separately for Parts A and B:

- All TEAEs
- Grade 3/4 TEAEs
- TEAEs by strongest relationship
- TEAEs by maximum severity
- TEAEs leading to treatment discontinuation
- TEAEs leading to treatment interruption
- Related TEAEs
- Serious TEAEs
- Related serious TEAEs

- TEAEs leading to death

Summaries will be presented separately for Parts A and B by MedDRA SOC and PT using frequency counts and percentages (i.e., number and percentage of subjects with an event) and the exposure adjusted event rate (except for summary by strongest relationship and maximum severity). When summarizing the number and percentages of subjects, subjects with multiple occurrences of the same adverse event or a continuing adverse event will be counted once, and only the maximum severity level will be presented in the severity summaries, and the strongest relationship level in the relationship summaries.

Additional summary tables separately for Parts A and B will be presented for TEAEs showing number, percentage of subjects, and the exposure adjusted event rate

- All TEAEs by PT

All AEs, including pretreatment AEs, TEAEs, and post-treatment AEs, will be presented in an individual subject data listing based on the All Subjects Set separately for Parts A and B. In addition, a listing containing individual subject adverse event data for TEAEs leading to treatment discontinuation, TEAEs leading to treatment interruption, Grade 3/4 TEAEs, SAEs and all deaths will be provided, with a flag indicating the TEAE status for SAEs and deaths for Parts A and B separately.

